3.3 Blinding and Randomization Methods

In the SAD Period of the study, all subjects receive open-label UX053. In the RD Period of the study, subjects are randomized 3:1 to UX053 and Placebo, using an interactive response technology (IRT) system. The RD Period of the study is double-blind. Each subject will be assigned a unique identification number.

Blind conditions will be established so that Ultragenyx, the subject, and site personnel will not know the identity of a subject's treatment during the RD Period of the study. The only unblinded Ultragenyx members, who will be involved, as needed, in the preparation of the unblinded DMC outputs, are the Independent Statistician, Independent Statistical Programmer and Independent PK Analyst.

Randomization using an IRT system will ensure subjects in the RD Period of the study are blind to treatment. Due to the difference in opacities of the UX053 and the placebo, an unblinded pharmacist will prepare the study drug and an unblinded nurse will prepare the infusion before masking the infusion syringe and tubing with colored covers. Prespecified employees from Ultragenyx who do not have any contact with the investigative sites may also be unblinded as specified in the Blinding Plan.

All imaging assessments will be sent to central readers for evaluation. Readers will be blinded to the subject's treatment.

Treatment assignment for an individual subject should be unblinded by the Investigator only in an emergency, and only if when knowledge of the treatment assignment is urgently needed for the clinical management or welfare of the subject. Unblinding at the study site for any other reason will be considered a protocol deviation.

The Investigator is strongly encouraged to contact Ultragenyx before unblinding any subject's treatment assignment, but priority should be given to the safety of the subject.

3.4 Stratification Factors

Not Applicable.

3.5 Sample Size Considerations

The sample size for this study is based on practical considerations and is consistent with a FIH study in a rare disease population. Approximately 26 to 30 subjects will enroll in this study, with a minimum of 10 subjects in the SAD period, 16 subjects in the RD period, and with the option to enroll additional subjects in any cohort to further characterize safety or PD findings. With at least 10 subjects receiving UX053 in the SAD Period, there is an 89% chance of detecting a more common AE given the TEAE has a true incidence of 20%. If at least 22 subjects receive UX053 in both SAD and RD Periods, there is a 90% chance of detecting a TEAE with true incidence of 10%.

Subjects will be replaced at Ultragenyx's discretion only if they have not received study drug. Subjects will not be replaced if they have received any study drug.

3.6 Data Monitoring Committee

An independent DMC will be constituted with experts in metabolic liver disease, GSD III, and/or immune activation and will act in an advisory capacity to Ultragenyx. Additionally, at least one of the DMC members will have expertise concerning statistical methods used in the design and analysis of clinical trials.

The DMC will meet and review study data at the frequency defined and in accordance with the scope and objectives set forth in the DMC Charter. The DMC may provide advice to Ultragenyx regarding the safety of subjects, the ethics of the study and the continuing scientific validity of the study. The DMC may also make recommendations to Ultragenyx concerning continuation, termination or other modifications of the study based on their

review of data. Further details regarding the DMC can be found in the DMC charter, which will be available prior to the administration of investigational product (IP).

Ultragenyx will review the DMC recommendations and determine necessary actions that will be communicated accordingly to all stakeholders, eg, Regulatory Authorities, IRBs/IECs, and Investigators.

3.7 Planned Analyses

Analyses are planned for each data review described in the study design (Section 3). During the SAD Period, an unblinded DMC will review at least 2 weeks of safety data for all subjects within a cohort before deciding to proceed with the next SAD cohort. During the RD Period, the unblinded DMC will review at least 6 weeks of safety from cohort 1R and all available data from prior cohorts before providing a recommendation for proceeding with cohort 2R. The same review and recommendation process will be used to determine the initiation for each of the remaining RD cohorts.

4 STUDY ENDPOINTS AND COVARIATES

The full schedule of assessments is shown in Appendix 12.4.

4.1 Primary Endpoint(s)

- The incidence and severity of TEAEs, serious TEAEs, and related TEAEs.

4.2 Secondary Endpoint(s)

- PK parameters of *AGL* mRNA and ATX95, including T_{max} , C_{max} , AUC_{last} , AUC_{inf} , T_{last} , $T_{1/2}$, CL , V_{ss} .

4.3 Tertiary Endpoints

4.3.1

- [REDACTED]
- [REDACTED]
- [REDACTED]
- [REDACTED]
- [REDACTED]

Term	Percentage
cooking oil	95
soybean oil	85
olive oil	80
sunflower oil	75
canola oil	70
margarine	65
butter	60
lard	55
shortening	50

4.3.2. PD/Efficacy Tertiary Endpoints

[REDACTED]

[REDACTED]

[REDACTED]

[REDACTED]

[REDACTED]

[REDACTED]

4.4 Exploratory Endpoints

[REDACTED]

[REDACTED]

4.5 Potential Covariate(s)

Not Applicable.

4.6 Subgroups

If a sufficient number of subjects with different disease subtypes (IIIa, IIIb, IIIc, and IIId) are enrolled, subgroup summaries by disease subtype may be provided at the discretion of Ultragenyx.

5 DEFINITIONS

5.1 Baseline

Baseline is defined as the last non-missing assessments prior to or on the date of initiation of the first dose of investigational product.

For nutrition diary data, baseline is defined as the average of all complete days (all values between screening and prior to dosing in SAD and between Stabilization Visit and prior to Dosing in RD). For CGM data, baseline is defined as the average of all daily measurements collected prior to the day of the first dose of IP administration.

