5.3 Study Day and Study Period

If the visit date is on or after the first dose of IP administration:

- Study day = visit date – date of the first dose of IP administration + 1.

If the visit date is prior to the first dose of IP administration:

- Study day = visit date – date of the first dose of IP administration.

There are three analysis periods in this study: Screening (data collected before the first IP dose), Treatment (from first IP dose up to two weeks after the last IP dose) and Follow-up Period (from two weeks after the last IP dose up to the last measurement in the study).

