7 STATISTICAL METHODS OF ANALYSES

7.1 General Principles

Descriptive statistics will be provided for selected demographics, safety, PK, and PD data. If a sufficient number of subjects with different disease subtypes are enrolled, subgroup summaries by disease subtype may be provided at the discretion of Ultragenyx. Continuous variables will be summarized by number of subjects and mean, SD and/or SE, median, minimum, and maximum values. Categorical variables will be summarized by number and percentage of subjects. Data will be summarized with descriptive statistics for the Screening Period.

The subject-level and cohort-level graphs of endpoints measurements over time will highlight the three periods of the study: Screening (data collected before the first IP dose), Treatment (from first IP dose up to two weeks after the IP dose) and Follow-up Period (from two weeks after the IP dose up to the last measurement in the study).

Although they are eligible, it is expected that few patients with GSD IIIb, IIIc, or IIId will enroll. Subjects with GSD IIIb/c/d will participate in all assessments, including muscle imaging and function tests, and will be included in all safety analyses. Sensitivity analyses for cardiac and skeletal muscle endpoints that exclude patients with GSD IIIb/c/d may be conducted.

The analysis will be presented by cohort and total group (Table 3). All raw data obtained from the CRFs will be included in data listings.

Table 2 Analysis Groups in the SAD Period

Cohort 1	Cohort 2	Total

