7.11 Analysis of Other Endpoints

7.11.1 Vital Signs

Descriptive statistics for vital signs (systolic and diastolic blood pressures, heart rate, respiration rate, temperature (C) and weight) and changes from baseline values at each visit and at the end of study will be presented by analysis group in each period. Individual subject listing and individual plots over time of vital signs parameters during dosing and separately over time for all visits will be provided.

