10.1.7 Visit Time Windows

For an unscheduled visit that occurred after the first dose date of IP, the unscheduled visit will be mapped into the closest post-baseline study scheduled visit for the assessment based on the study day of the unscheduled visit, and the target study day of the scheduled visit of the assessment in the protocol. If the unscheduled visit has equal distance to the 2 study scheduled visits, it will be mapped to the later visit.

The unscheduled visit will be only mapped to study visit within each period during it occurs.

When there is more than 1 measurement mapped to the same scheduled visit (including the original measurement taken from the scheduled visit), the measurement taken on the scheduled visit will be used if it is not missing, otherwise the visit closest to the target day will be used. If more than 1 visit has equal distance to the target day, then the later visit will be used. If more than 1 measurement is collected on the same day, the time or sequence

number will be used to select the latest record. For listings and shift tables, all data points will be included.

Early termination visit will follow the same rule for unscheduled visit as described above.

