AGL, amylo- α -1,6-glucosidase 4-alpha-glucanotransferase; AH50, alternative complement activity; BL, baseline; BNP, B-Type Natriuretic Peptide; CGM, continuous glucose monitor; CH50, classical pathway complement activity; CK, creatinine kinase; CK-M/B, CK-muscle/brain; COVID-19, coronavirus disease 2019; CRP, C-reactive protein; D, day; ECG, electrocardiogram; EOS, end of study; ET, early termination; GDE, glycogen debranching enzyme; Glc4, glucose tetrasaccharide; GSD, glycogen storage disease; GNEM-FAS, GNE Myopathy Functional Activities Scale; HHD, handheld dynamometry; HHG, handheld glucometer; HDL, high density lipoprotein; IL-6, interleukin-6; LDL, low density lipoprotein; MRI, magnetic resonance imaging; MRS, magnetic resonance spectroscopy; PROMIS, Patient-Reported Outcomes Measurement Information System; PBMC, peripheral blood mononuclear cell; PK, pharmacokinetic; PT/INR, prothrombin time/international normalized ratio; sC5b-9, soluble Complement 5b-9; SF-36v2, Short Form Health Survey 36 Version 2.

Table 6: Schedule of Vital Sign Assessments

Study Period	SAD Period	RD Period				
Time	Day 0	Week 0	Week 2	Week 4	Week 6	Week 8
Pre-Infusion						
Within 30 min of initiating the infusion	X	X	X	X	X	X
During infusion (4 hr infusion)						
15 min (\pm 5 min)	X	X	X	X	X	X
30 min (\pm 5 min)	X	X	X	X	X	X
45 min (\pm 5 min)	X	X	X	X	X	X
1 hr (\pm 10 min)	X	X	X	X	X	X
2 hr (\pm 10 min)	X	X	X	X	X	X
3 hr (\pm 10 min)	X	X	X	X	X	X
4 hr (\pm 10 min)	X	X	X	X	X	X
Post-infusion (24 hr monitoring)^a						
5 hr (\pm 5 min)	X	X	X	X	X	X
6 hr (\pm 5 min)	X	X	X	X	X	X
7 hr (\pm 10 min)	X	X	X	X	X	X
8 hr (\pm 10 min)	X	X	X	X	X	X
9 hr (\pm 10 min)	X	X	X	X	X	X
10 hr (\pm 10 min)	X	X	X	X	X	X
16 hr (+/- 1hr)	X	X	X	X	X	X
24 hr (+/- 2hr)	X	X	X	X	X	X

hr, hour; min, minute; RD, Repeat Dose; SAD, Single Ascending Dose.

^a All post-infusion time points refer to time from the beginning of the infusion.

Table 7: Schedule of PK Assessments during and following Treatment Infusion

Study Period	SAD Period		RD Period			
Sample Type	Blood	Plasma	Blood	Plasma	Blood	Plasma
Analyte	AGL mRNA	ATX95	AGL mRNA	ATX95	AGL mRNA	ATX95
Infusion	Day 0 Infusion		Week 0 Infusion		Week 8 Infusion	
Pre-infusion						
Within 1 hr prior to initiating infusion	X	X	X	X	X	X

During infusion (4 hr infusion)						
1 hr (± 10 min) ^a	X	X	X	X	X	X
3 hr (± 10 min)	X	X	X	X	X	X
Post-infusion						
4 hr (± 10 min) ^b	X	X	X	X	X	X
4.5 hr (± 10 min)	X	X	X	X	X	X
5 hr (± 10 min)	X	X	X	X	X	X
6 hr (± 20 min)	X	X	X	X	X	X

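### The SAP sets baseline by calendar date with no pre-dose limit, so vital-sign changes in all 8 SAD subjects are measured against a reading taken after the infusion started

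*SAP*

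**What the plan says.** - **General rule (SAP 5.1).** "Baseline is defined as the last non-missing assessments prior to or on the date of initiation of the first dose of investigational product". No clock time or pre-dose condition is attached.
- **Exceptions (SAP 5.1).** The nutrition-diary baseline ends before dosing. The CGM baseline uses measurements "collected prior to the day of the first dose of IP administration". Vital signs have no such exception.
- **Study day and windows.** SAP 5.3 makes the dosing date study day 1, and the window table in SAP 10.4 assigns study days up to and including 1 to Baseline. When one day holds several measurements, SAP 10.1.7 says a time or sequence "number will be used to select the latest record".
- **Periods (SAP 5.3).** Screening data are those before the first dose; the next period is "Treatment (from first IP dose up to two weeks after the last IP dose)".
- **Vital-sign schedule (SAP Table 6; Protocol Table 7).** There is one reading within 30 minutes before the infusion, then readings at 15, 30 and 45 minutes, hourly from 1 to 10 hours, and at 16 and 24 hours. "All post-infusion time points refer to time from the beginning of the infusion".
- **Analysis (SAP 7.11.1).** For vital signs, "changes from baseline values at each visit and at the end of study will be presented by analysis group in each period".
- **Who is analysed (SAP 8).** Four subjects in Cohort 1S and four in Cohort 2S.

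**The concern.** A baseline should describe the subject before exposure. A rule that takes the last value on the dosing date, for a measurement repeated through the infusion and for hours afterwards, returns a value recorded under treatment. SAP 5.3 itself places that value in the Treatment period.

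The same number is subtracted at every later visit, so the error carries through the whole follow-up. Safety is the primary objective, and Protocol 5.4.1 lists tachycardia and raised body temperature among the possible signs of immune activation. If either is still present at the selected reading, later values will appear to fall below baseline when they have only returned to it. With 4 subjects per cohort, one such subject moves the cohort mean by a quarter of that subject's shift.

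**Working it through.** **1. Does any SAP rule lead back to the pre-infusion reading?**

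| Text | Effect on Day 0 vital signs |
|---|---|
| SAP 5.1, general rule | Last value on or before the dosing date |
| SAP 5.3 with 10.4 | Dosing date = study day 1, inside the Baseline window |
| SAP 10.1.7, preference for the scheduled visit | No help: every timed reading belongs to the scheduled Day 0 visit |
| SAP 10.1.7, several values on one day | Latest record |
| SAP Table 4 footnotes | Weight, ECG, chemistry and hematology on Day 0 are marked as pre-dose; vital signs are instead referred to the schedule during dosing |
| SAP 5.3, periods | Implies that post-start values are not pre-treatment, but is not written as a baseline rule |

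None does. The protocol gives no baseline definition with a pre-dose limit to fall back on, and SAP 1 gives the SAP precedence on analysis.

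**2. Which reading is selected?** The documents give no clock time for the infusion, so start times are assumed. For start s, keep the scheduled times t (0.25, 0.5, 0.75, 1, 2, ..., 10, 16, 24 h) with s + t before 24:00, and take the last.

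| Assumed start | Post-start readings on that date | Selected reading |
|---|---|---|
| 07:00 | 14 | 16 h (7 + 16 = 23:00) |
| 08:00 to 13:59 | 13 | 10 h |
| 14:00 | 12 | 9 h |
| 15:00 | 11 | 8 h |
| 16:00 | 10 | 7 h |
| 21:00 | 5 | 2 h |
| 22:00 | 4 | 1 h |

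These are nominal times. The permitted tolerances move the selection by at most one scheduled reading; for example, the 16 h reading may be taken 1 h early, so after an 08:30 start it can still fall on the dosing date. No start time in the assumed range of 06:00 to 23:00 yields the pre-infusion reading when the scheduled readings are present.

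**3. Size of the error.** Let d = selected reading - pre-infusion reading. Then reported change = (later value - pre-infusion) - d, a shift of -d. The documents give no value for d. Over an assumed range for heart rate, with a true change of 0:

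- d = +5 bpm is reported as -5
- d = +10 bpm is reported as -10
- d = +20 bpm is reported as -20

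The shift recurs at 7 post-dose visits in Protocol Table 4 (D1, D4, D7, D14, D21, D28, D90), or 8 in the SAP schedule, which retains D42. It affects 5 of the 6 parameters in SAP 7.11.1 (not weight) in 4 + 4 = 8 subjects.

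**4. Conditional extension to biomarkers.** CH50, AH50, sC5b-9, IL-6, fibrinogen and d-dimer are sampled on Day 0 before dosing and at the end of infusion. If the general rule governs them, the end-of-infusion sample is the baseline. With r = end of infusion / pre-dose (assumed), and Day 1 back at the pre-dose level, the reported end-of-infusion change is 0% and the reported Day 1 change is 1/r - 1:

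| r | True end-of-infusion change | Reported | True Day 1 change | Reported |
|---|---|---|---|---|
| 0.5 | -50% | 0% | 0% | +100% |
| 1.5 | +50% | 0% | 0% | -33% |
| 2 | +100% | 0% | 0% | -50% |
| 3 | +200% | 0% | 0% | -67% |

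**5. With a pre-start limit**, the baseline is the pre-infusion reading, or an earlier one if that is missing, whatever the start time. None of the 8 subjects then has a post-start baseline.

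**The case against.** The strongest reply is that a pre-dose baseline was plainly intended. The diary and CGM rules stop before dosing or before the dosing day, SAP 5.3 and 7.1 end Screening at the first dose, and SAP 10.1.7 is mainly about mapping unscheduled visits, which it confines to the period in which they occur. A programmer might well use the pre-infusion value, and the documents do not show what was programmed. All of that stands as evidence of intent. It does not supply a cut-off: the general rule omits the limit that its two neighbours contain, and the visit rules point the same way as its wording.

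Other points stand as limits on size. Start times and d are assumed. Protocol 7.1.4 says that toxicities in the nonclinical studies generally appeared soon after dosing and resolved promptly, so a 10-hour reading may differ little from the pre-infusion one; if d is 0 there is no shift. The summaries are descriptive. The acute data remain visible, since SAP 7.1 states "All raw data obtained from the CRFs will be included in data listings" and SAP 7.11.1 provides "individual plots over time of vital signs parameters during dosing". Protocol 10.1.2 also has new, clinically significant vital-sign abnormalities captured as AEs.

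The biomarker part rests on text that is partly blacked out. No visible SAP section specifies a change-from-baseline analysis for those markers; the link is the general laboratory sentence in Protocol 11.4. It must stay conditional.

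**Conclusion.** The rule is wrong as written. Applied literally, it gives all 8 SAD subjects an on-treatment baseline for five vital signs, nominally at least 2 hours after the start for any infusion begun by 21:00 and 10 hours after for starts from 08:00 to 13:59. Every later change is shifted by -d. The selection follows from the SAP text and schedule and assumes that the scheduled readings were taken; the exact lag depends on the assumed start time, and the size of d is unknown. The effect is confined to change-from-baseline summaries: TEAE incidence does not use this baseline. The extension to complement, IL-6, fibrinogen and d-dimer holds only if no blacked-out section defines their baseline separately. This should be fixed, but it does not threaten the primary endpoint.

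**What to change.** - **SAP 5.1.** Replace the general rule with: *Baseline is the last non-missing assessment before the start of the first infusion of investigational product, identified by recorded time or, where no assessment time is recorded, by the scheduled pre-dose or pre-infusion label.*
- **SAP 10.1.7 and 10.4.** Exclude dosing-day records taken after the infusion started from the Baseline window, and summarise them under their own nominal time points (15 minutes to 24 hours; end of infusion).
- **Biomarkers.** If a separate baseline for complement, IL-6, fibrinogen and d-dimer exists elsewhere in the SAP, refer to it from 5.1.

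The cost is one sentence and one exclusion. Protocol 9.7 already records infusion start and stop times in the CRF. The documents do not show that clock times of vital signs or samples are recorded, but the nominal labels in the schedules are sufficient.

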10.1.5. Safety Laboratory Tests

Blood and urine samples will be collected for safety laboratory tests as specified in [Table 4](#), [Table 5](#), and [Table 6](#). Fasting is not required. For visits in which subjects are receiving study drug, laboratory samples will be collected prior to dosing. All efforts should be made for urine collections to be from the first morning void. Samples will be processed by a central lab to ensure consistency across study sites.

In addition to chemistry, hematology, and urinalysis, additional assessments to monitor safety include activation of the complement pathway, coagulation factors, and interleukin-6. As noted in [Table 4](#), [Table 5](#), and [Table 6](#), samples for complement pathway, coagulation factors, and interleukin-6 are collected pre- and post-infusion. Post-infusion blood samples should be collected in the opposite arm of the infusion to avoid laboratory artefacts. The full list of safety laboratory evaluations to be performed in this study are listed in [Appendix 3](#). All laboratory samples listed in [Appendix 3](#) will be processed by a central laboratory, except urine pregnancy.

The study site should indicate to laboratories if the subject is taking high dose biotin supplements (found in multivitamins, biotin supplements, and some supplements to promote hair, skin, and nail growth) to potential risk of assay interference (eg, troponin) ([FDA, 2019a](#)).

The Investigator (and/or Medical Monitor) may at his/her discretion perform additional laboratory tests for subject safety if a subject experiences an SAE or other AE that may warrant further follow up.

Close monitoring is required for subjects who develop elevations in ALT > 3x ULN and > 2x their baseline value, or elevation in ALT > 3x ULN with INR > 1.5. This includes repeating liver enzymes and INR within 48 hours and consideration of additional diagnostic tests such as liver ultrasound.

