Clinical laboratory data will be summarized by the type of laboratory test and by changes from baseline. Reference ranges and abnormal results (specified in the SAP) will be used in the summary of laboratory and ECG data. The frequency and percentage of subjects who experience abnormal clinical laboratory results (ie, outside of reference ranges) and/or clinically significant abnormalities (as determined by the Investigator) will be presented for each clinical laboratory measurement, including for Hy's Law analysis (ALT, AST, total and direct bilirubin, ALP). Shift tables may be provided for changes from baseline in selected chemistry and hematology laboratory parameters. Listings of abnormal vital signs and physical findings will be provided. The SAP will provide additional details on the planned safety analyses. Several safety laboratory tests will also be examined for efficacy (Section 11.7).

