^d Assessments to be performed prior to dosing. The following assessments can be collected within a week prior to dosing, as long as there is 10 to 14 days between assessments that are repeated at the Screening Visit and the Baseline Visit: HHD, PROMIS questionnaires, SF-36v2, and GNEM-FAS expanded version.

^e Refer to Table 6 for the timing of vital sign assessments during dosing.

^f Refer to Table 7 for details of PK sampling. Please note that sample collections are marked for D1, D4, D7, D14, D21, and D28 in this table (Table 4) corresponding to a sample collection 1, 4, 7, 14, 21, and 28 days after infusion of UX053 on D0 as outlined in the final rows of the first column in Table 7.

^g Sample to be collected pre-dose and at the end of the infusion. Post-infusion blood samples should be collected in the opposite arm of the infusion to avoid dilution.

^h Close monitoring is required for subjects who develop elevations in ALT > 3x ULN and > 2x their baseline value, or elevation in ALT > 3x ULN with INR > 1.5. This includes repeating liver enzymes and INR within 48 hours and consideration of additional diagnostic tests such as liver ultrasound (Section 10.1.5).

ⁱ All efforts should be made for urine collections to be consistently taken from the first morning void.

^j Liver and calf MRS are only required at sites with capability. Scanning for liver and calf MRS can be conducted immediately following the liver MRI.

^k A 3 to 4 hour fasting period is preferred, but not required, prior to blood collection for serum HDL and LDL. All efforts should be made to obtain samples for HDL and LDL consistently for a given subject.

^l The nutrition diary recordings should be recorded daily from the Screening Visit through the EOS I D90/ET Visit.

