10.4 Visit Window Example

SAD period:

Visit	Scheduled Visit Day	Window
Baseline	Day 0	≤ 1
Day 1	Day 1	[2]
Day 4	Day 4	[3, 5]
Day 7	Day 7	[6, 10]
Day 14	Day 14	[11, 17]
Day 21	Day 21	[18, 24]
Day 28	Day 28	[25, 34]
Day 42	Day 42	≥ 35

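### SAP 5.1 sets baseline by calendar date, so read literally it takes a vital-sign reading made after infusion start as the baseline

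*SAP*

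**What the plan says.** The general rule in SAP 5.1 is: "Baseline is defined as the last non-missing assessments prior to or on the date of initiation of the first dose of investigational product". The same section then sets two special rules that do stop before treatment. Nutrition-diary values must precede dosing, and the CGM baseline is "the average of all daily measurements collected prior to the day of the first dose of IP administration". Only the general rule has no such limit.

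In SAP Table 4, most Day 0 assessments carry footnote d, which requires them before dosing. Two groups do not:

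- **Vital signs** carry footnote e, which points to Table 6 "for the timing of vital sign assessments during dosing". SAP Table 6 and Protocol Table 7 list one pre-infusion reading and 15 later ones, counted from the beginning of the infusion.
- **CH50, AH50, sC5b-9, IL-6, fibrinogen and d-dimer** carry footnote g: "Sample to be collected pre-dose and at the end of the infusion". Protocol 10.1.5 agrees: "samples for complement pathway, coagulation factors, and interleukin-6 are collected pre- and post-infusion".

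The baseline is then used in two places. SAP 7.11.1 tabulates vital-sign changes from baseline at each visit and at end of study. For laboratory tests, Protocol 11.4 says: "Clinical laboratory data will be summarized by the type of laboratory test and by changes from baseline".

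SAP 8 limits the analysis to cohorts 1S and 2S, with four subjects each.

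**The concern.** A baseline should describe the subject before treatment. A rule that runs to the end of the dosing date is harmless for a test done only before dosing. It fails for a test repeated after the infusion has begun, because the last value of the day is then a treated value. Vital signs are the clear case: they are repeated on the dosing day, and a change-from-baseline table for them is planned in readable text.

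At stake is the reference value subtracted at every later visit. Safety is the primary objective, and Protocol 10.1 evaluates it partly through changes from baseline in vital signs and laboratory values. With four subjects per cohort, one distorted baseline carries a quarter of the weight in a cohort mean. Two programmers could also read the SAP differently and produce different tables.

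**Working it through.** The plan gives no figure to reproduce here. The check applies the SAP 5.1 rule, as worded, to the Day 0 schedule.

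**1. Which assessments are exposed.** Only those scheduled again on the dosing date after infusion start, without the pre-dose footnote: vital signs and the six markers above. Weight, ECG and the standard laboratory panels are pre-dose on Day 0. The Day 0 cell for PT/INR is also pre-dose. The SAP's row label for PT/INR shows footnote g, where Protocol Table 4 has the close-monitoring footnote; I take this as a lettering slip and leave PT/INR out.

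**2. Vital-sign times after start** (SAP Table 6, Protocol Table 7): 15, 30 and 45 minutes (3), hourly from 1 to 10 hours (10), 16 hours (1) and 24 hours (1). Total 3 + 10 + 1 + 1 = 15.

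**3. Which reading the rule picks.** A reading falls on the dosing date if start + t < 24:00, using nominal times. The documents do not give the start time, so the values below are assumptions.

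| Assumed start | Post-start readings on dosing date | Reading selected (h after start) | Hours after a 4-hour infusion ends |
|---|---|---|---|
| 07:00 | 14 of 15 | 16 | 12 |
| 08:00–13:59 | 13 of 15 | 10 | 6 |
| 14:00 | 12 of 15 | 9 | 5 |
| 15:00 | 11 of 15 | 8 | 4 |

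The earliest post-start reading, at 15 minutes, falls on the dosing date for any start before 24:00 − 0:15 = 23:45. Before that time the pre-infusion reading is never the last one.

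**4. Effect on the tables.** Let P be the pre-infusion reading, x the residual infusion effect in the selected reading, and V a later visit value.

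- Intended change: V − P.
- Reported change: V − (P + x) = (V − P) − x.

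Each later change for that subject shifts by −x. If one of four subjects is affected, the cohort mean change shifts by −x/4. This applies at all post-dose visits: 7 in Protocol Table 4 (Days 1, 4, 7, 14, 21, 28 and 90), or 8 in SAP Table 4, which keeps Day 42. Once the effect has worn off, the true change is zero and the table shows −x.

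**5. The six markers.** With a 4-hour infusion, the end-of-infusion sample is on the dosing date for any start before 24:00 − 4:00 = 20:00. The literal rule then selects it over the pre-dose sample: 6 analytes × 8 subjects = 48 baselines, if no analyte-specific rule applies.

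**6. Does other SAP text settle it?**

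- SAP 5.3 makes the dosing date study day 1, and SAP 10.4 sets the Baseline window at study day ≤ 1. The window therefore covers the whole dosing date and does not exclude post-start readings.
- SAP 5.3 and 7.1 define periods by dose, the first being "Screening (data collected before the first IP dose". That points to a pre-dose value, but neither section ties baseline to the Screening period.

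**The case against.** The best reply is that everyone will use the pre-dose value. A reading taken 10 hours after infusion start is Treatment data under SAP 5.3 and 7.1, so using it as baseline would clash with the SAP's own periods. Table 6 labels a separate pre-infusion reading, and SAP 7.11.1 plots during-dosing readings apart from visit data. This stands as evidence of intent, and a pre-dose baseline is very likely what was meant. It does not change the rule as written: the link from period to baseline is never made, and SAP 1 gives the SAP precedence over the protocol on analysis.

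Some supporting text is weaker than it looks. SAP 10.4 is headed as an example and works in whole days, so it cannot separate pre-dose from post-dose on day 1. The instruction in SAP 10.1.7 to take the latest same-day record concerns visit mapping, not baseline. Neither shows that a post-infusion baseline was intended.

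A reader might also infer that the acute rise in complement, cytokine and coagulation markers will be reported as zero, because the end-of-infusion value would be its own reference. The documents do not support going that far. The only readable basis for a change-from-baseline analysis of these markers is one general sentence in Protocol 11.4. SAP 5.5–5.12 and 7.9 are redacted and may hold specific rules. No readable text plans an end-of-infusion summary in which such a zero would appear.

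Finally, the effect may be small. Protocol 7.1.4 reports that nonclinical toxicities generally resolved promptly, and for starts of 08:00–13:59 the selected reading is 6 hours after a 4-hour infusion ends. That limits the likely size but does not make the reference value correct.

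**Conclusion.** Wrong as written. Followed literally, SAP 5.1 uses a vital-sign reading taken after infusion start as baseline for any start before 23:45, and that value enters the tables planned in SAP 7.11.1. The bias is −x per affected subject and −x/4 in the mean of a four-subject cohort when one subject is affected. The documents give no value for x, and it may be small.

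For the six markers the conclusion is conditional. The rule selects the end-of-infusion sample for a 4-hour infusion starting before 20:00, provided no redacted rule overrides it.

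A reader might infer that the primary safety result is compromised, or that infusion reactions would be hidden. Neither follows. The primary endpoint is treatment-emergent adverse events, whose capture does not use this baseline. Raw data are listed, and individual during-dosing plots of vital signs are planned. Nor would a treated baseline simply erase an effect from later visits: after the effect has resolved, it creates an apparent change of opposite sign.

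The conclusion rests on nominal reading times, a 4-hour infusion for the marker samples, and the readable SAP text.

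**What to change.** In SAP 5.1, add one sentence: for any assessment repeated on the dosing day, baseline is the last non-missing value before the start of the first infusion, and later same-day readings or samples are post-baseline. In SAP 10.4, note that on study day 1 the Baseline window covers only pre-infusion values. If a redacted section already sets a rule for the six markers, check that it agrees.

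With this change the baseline is the pre-infusion vital-sign reading and the pre-dose marker sample, whatever the start time. The cost is two lines of text, with no new data, visits or analyses.
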